8.3 ADVERSE EVENTS AND SERIOUS ADVERSE EVENTS

8.3.1 DEFINITION OF ADVERSE EVENTS (AE)

Adverse event means any untoward medical occurrence associated with the use of a drug in humans, whether or not considered drug related (21 CFR 312.32 (a)).

8.3.2 DEFINITION OF SERIOUS ADVERSE EVENTS (SAE)

An adverse event or suspected adverse reaction is considered "serious" if, in the view of either the investigator or sponsor, it results in any of the following outcomes: death, a life-threatening adverse event, inpatient hospitalization or prolongation of existing hospitalization, a persistent or significant incapacity or substantial disruption of the ability to conduct normal life functions, or a congenital anomaly/birth defect. Important medical events that may not result in death, be life-threatening, or require hospitalization may be considered serious when, based upon appropriate medical judgment, they may jeopardize the participant and may require medical or surgical intervention to prevent one of the outcomes listed in this definition. Examples of such medical events include allergic bronchospasm requiring intensive treatment in an emergency room or at home, blood dyscrasias or convulsions that do not result in inpatient hospitalization, or the development of drug dependency or drug abuse.

8.3.3 CLASSIFICATION OF AN ADVERSE EVENT

The National Cancer Institute's Common Terminology Criteria for Adverse Events (CTCAE) version 5.0 will be used to classify Adverse Events when possible.

8.3.3.1 SEVERITY OF EVENT

All Adverse Events (AEs) will be assessed by the study clinician and classified and graded for severity using the National Cancer Institute's Common Terminology Criteria for Adverse Events (CTCAE) version 5.0 when possible. The GpCRC Medical Safety Officer was involved in deciding which grading system to use for the GpCRC.

For AEs not included in the protocol defined grading system, the following guidelines will be used to describe severity.

- **Mild** – Events require minimal or no treatment and do not interfere with the participant's daily activities.
- **Moderate** – Events result in a low level of inconvenience or concern with the therapeutic measures. Moderate events may cause some interference with functioning.
- **Severe** – Events interrupt a participant's usual daily activity and may require systemic drug therapy or other treatment. Severe events are usually potentially life-threatening or incapacitating. Of note, the term "severe" does not necessarily equate to "serious".

8.3.3.2 RELATIONSHIP TO STUDY INTERVENTION

All adverse events (AEs) must have their relationship to study intervention assessed by the clinician who examines and evaluates the participant based on temporal relationship and his/her clinical judgment.

The degree of certainty about causality will be graded using the categories below. In a clinical trial, the study product must always be suspect.

- **Definitely Related** – There is clear evidence to suggest a causal relationship, and other possible contributing factors can be ruled out. The clinical event, including an abnormal laboratory test result, occurs in a plausible time relationship to study intervention administration and cannot be explained by concurrent disease or other drugs or chemicals. The response to withdrawal of the study intervention (dechallenge) should be clinically plausible. The event must be pharmacologically or phenomenological definitive, with use of a satisfactory rechallenge procedure if necessary.
- **Probably Related** – There is evidence to suggest a causal relationship, and the influence of other factors is unlikely. The clinical event, including an abnormal laboratory test result, occurs within a reasonable time after administration of the study intervention, is unlikely to be attributed to concurrent disease or other

drugs or chemicals, and follows a clinically reasonable response on withdrawal (dechallenge). Rechallenge information is not required to fulfill this definition.

- **Potentially Related** – There is some evidence to suggest a causal relationship (e.g., the event occurred within a reasonable time after administration of the trial medication). However, other factors may have contributed to the event (e.g., the participant's clinical condition, other concomitant events). Although an AE may rate only as "possibly related" soon after discovery, it can be flagged as requiring more information and later be upgraded to "probably related" or "definitely related", as appropriate.
- **Unlikely to be related** – A clinical event, including an abnormal laboratory test result, whose temporal relationship to study intervention administration makes a causal relationship improbable (e.g., the event did not occur within a reasonable time after administration of the study intervention) and in which other drugs or chemicals or underlying disease provides plausible explanations (e.g., the participant's clinical condition, other concomitant treatments).
- **Not Related** – The AE is completely independent of study intervention administration, and/or evidence exists that the event is definitely related to another etiology. There must be an alternative, definitive etiology documented by the clinician.

8.3.3.3 EXPECTEDNESS

The Study Physician will be responsible for determining whether an AE is expected or unexpected. An AE is considered "unexpected" if it is not listed in the Investigator Brochure or is not listed at the specificity or severity that has been observed; "unexpected," as used in this definition, also refers to AEs or suspected adverse reactions that are mentioned in the Investigator Brochure as occurring with a class of drugs or as anticipated from the pharmacological properties of the drug, but are not specifically mentioned as occurring with the particular drug under investigation.

8.3.4 TIME PERIOD AND FREQUENCY FOR EVENT ASSESSMENT AND FOLLOW-UP

The occurrence of an AE or serious adverse event (SAE) may come to the attention of study personnel during study visits and interviews of a study participant presenting for medical care, or upon review by a study monitor.

All AEs including local and systemic reactions not meeting the criteria for SAEs will be captured on the appropriate case report form. Information to be collected includes event description, time of onset, clinician's assessment of severity, relationship to study product (assessed only by those with the training and authority to make a diagnosis), and time of resolution/stabilization of the event. All AEs occurring while in the study must be documented appropriately regardless of relationship. All AEs will be followed to adequate resolution.

Any medical condition that is present at the time that the participant is screened will be considered as baseline and not reported as an AE unless the AE results from a study procedure performed during screening. However, if the study participant's condition deteriorates at any time during the study, it will be recorded as an AE.

Changes in the severity of an AE will be documented to allow an assessment of the duration of the event at each level of severity to be performed. AEs characterized as intermittent require documentation of onset and duration of each episode.

The Study Physician and Clinical Coordinator will record all reportable events with start dates occurring any time after informed consent is obtained until 7 (for non-serious AEs) or 30 days (for SAEs) after the last day of study participation. At each study visit, the investigator will inquire about the occurrence of AE/SAEs since the last visit. Events will be followed for outcome information until resolution or stabilization.

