9.2 SAMPLE SIZE DETERMINATION

Summary of sample size and computation of primary outcome:

The primary outcome variable is change in the PAGI-SYM postprandial fullness/early satiety subscore from baseline to 4 weeks. This subscore is calculated by averaging the scores for 4 PAGI-SYM items: stomach fullness, inability to finish a normal-sized meal, feeling excessively full after meals, and loss of appetite. Each item score ranges from 0 (none) to 5 (very severe) on an ordinal scale. The 4-item average is treated as continuous in the primary ANCOVA analysis of change and for sample size purposes.

The planned 108 participants sample size for this trial was derived using the following assumptions and methods:

- 2 equal size groups
- Power=90%
- Type 1 error (2-sided) = 0.05
- Two-sided tests
- Sample size increased by 10% to allow for 10% loss in primary outcome measure
- Placebo group assumptions: Based on the APRON RCT placebo data [9], we assumed that:
 - Mean (SD) change in postprandial fullness/early satiety subscore at 4-weeks = 3.7 (0.8)
 - Change from baseline at 4-weeks of fullness/early satiety subscore = -0.7 (1.0)
 - Correlation of postprandial fullness/early satiety subscore at baseline and 4-weeks = 0.55
- Method of analysis = ANCOVA of the change in the primary outcome score controlling for baseline value of the primary outcome score
- Intention-to-Treat Analysis using all randomized participants, corrected for missing outcome data:
 - Multiple imputation of the ANCOVA model using the chained equations method with 50 imputations using the Stata Software Command: *mi*
- Minimal Clinical Important Difference (MCID) = 0.62 SD (0.5 subscore points)
- Sample size software: Stata Software Command: *power repeated*
- **Sample size = 108 total (54 per group)**

Sample size for the primary outcome varying the MCID

MCID in SD units	0.3 SD	0.50 SD	0.62 SD*	1 SD
MCID subscore units	0.24	0.4	0.5	0.8
Total sample size	460	168	108	42
Number per group	230	84	54	21

* MCID between investigator-related severity and fullness/early satiety subscore range=0.62-0.70 SD [25]

For the key secondary outcome, symptom improvement by 1-point or more in the PAGI-SYM GSCI total score from baseline to week 4, we determined that the total sample size of 108 participants (54 per group) gives 80% power to detect an MCID for a relative improvement ratio=1.8 (60% buspirone vs. 32% placebo based on APRON

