9.4.4 SAFETY ANALYSES

Safety data will be presented by treatment group to the Data and Safety Monitoring Board during the course of the trial. Each adverse event will be displayed showing AE name per the CTCAE v5.0 when applicable, class, severity grade, random patient ID, clinic, treatment group, time since randomization, resolution status and physician’s assessment of relatedness to treatment. Participant-specific summary tables including any adverse event (yes vs no), frequency of multiple adverse events (i.e., 0, 1, 2, 3+) and highest severity grade of adverse event (none, mild, moderate, severe, life-threatening) will be displayed by treatment group along with p-values from Fisher’s exact tests.

In addition, rates of adverse events and hospitalizations will be reported between treatment groups, both by number of events and by participant. Count data will be analyzed using a negative binomial model accounting for over-dispersion of the count data.

Other safety data to be monitored include baseline levels and changes in laboratory measures, weight, and ECG results. These will be compared between treatment groups using ANCOVA models for change in measures or Fisher’s Exact Tests for categorical outcomes.

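### The by-arm adverse event tests pool worsening of gastroparesis with all other events, which shifts them toward showing no excess on buspirone if the drug works

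*Combined protocol and SAP*

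**What the plan says.** Section 8.3.4 sets the recording rule in two steps. First: "Any medical condition that is present at the time that the participant is screened will be considered as baseline and not reported as an AE". Then: "However, if the study participant's condition deteriorates at any time during the study, it will be recorded as an AE". It makes no exception for the disease under study. It also says "All AEs occurring while in the study must be documented appropriately regardless of relationship", so attribution to the underlying disease does not keep an event off the list. Section 8.3.8, on events of special interest, is marked not applicable.

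Section 9.4.4 specifies the comparisons. At participant level it plans "Participant-specific summary tables including any adverse event (yes vs no), frequency of multiple adverse events" and highest grade, each by arm with Fisher's exact test. At event level, "rates of adverse events and hospitalizations will be reported between treatment groups, both by number of events and by participant", with a negative binomial model for counts. None of these separates worsening of gastroparesis from other events.

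The same section also describes a listing for the monitoring board: "Each adverse event will be displayed showing AE name per the CTCAE v5.0 when applicable, class, severity grade, random patient ID, clinic, treatment group", together with the physician's "assessment of relatedness to treatment". Separately, section 8.2 describes a side-effect questionnaire covering headache, dizziness, drowsiness and similar complaints. The schedule of activities places it at screening and at weeks 2, 4 and 6, and side-effect frequency is part of secondary outcome 14. Section 9.4.4 names no analysis of it, and the hypotheses in 9.1 stop at item 10.

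**The concern.** Eligibility requires a fullness/early satiety subscore of at least 3 and a GCSI total above 2.0, so every participant has the symptoms whose worsening 8.3.4 makes an adverse event. More fullness, nausea, vomiting, bloating or upper abdominal pain is the primary or a secondary efficacy outcome with its sign reversed.

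Randomization and masking do not remove the problem. If the primary hypothesis is true, the placebo arm has more of these events because buspirone works, and that surplus offsets events the drug causes. The shift is largest when efficacy is shown, which is also when the tolerability statement carries most weight. If buspirone does not work, the pooled tests are not shifted, but they are diluted by events common to both arms. Safety and tolerability is a stated secondary objective.

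**Working it through.** **Inputs from section 9.2.** Placebo: "Change from baseline at 4-weeks of fullness/early satiety subscore = -0.7 (1.0", the bracketed figure being the SD. Design effect 0.5 points, two-sided alpha 0.05, power 90%, 54 per arm.

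**The plan's own figure.** With SD 0.8 and correlation 0.55, the change-score SD is 0.8 × √(2 × 0.45) = 0.759. For a 0.5-point difference at 90% power this gives 49 per arm; × 1.1 = 54 per arm, 108 in total. The stated sample size reproduces. The plan states no figure for the adverse event comparison.

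**Step 1: worsening implied by the design figures.** With normal changes, P(change > t) = 1 − Φ(t + 0.7) on placebo and 1 − Φ(t + 1.2) on buspirone.

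| Rise in subscore | Placebo | Buspirone |
|---|---|---|
| above 0 | 24.2% | 11.5% |
| above 0.5 | 11.5% | 4.5% |
| above 1.0 | 4.5% | 1.4% |

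With the 0.759 SD instead of 1.0, the first row is 1 − Φ(0.7/0.759) = 17.8% against 1 − Φ(1.2/0.759) = 5.7%. The gap between arms is about the same (12.1 against 12.7 points).

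**Step 2: assumptions not in the documents.** Other adverse events occur in 35% on placebo and 55% on buspirone, independently of worsening. A share s of the rises is recorded as adverse events. Then P(any event) = 1 − (1 − other)(1 − s × worsening). Example for s = 1 and any rise: placebo 1 − 0.65 × 0.758 = 50.7%; buspirone 1 − 0.45 × 0.885 = 60.2%; difference 9.5 points.

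**Step 3: exact power of the two-sided Fisher test, 54 per arm, counting only rejections toward more events on buspirone.**

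| Recorded as adverse events | Difference, drug effective | Power, drug effective | Power, no efficacy |
|---|---|---|---|
| none (worsening separated) | 20.0 points | 46% | 46% |
| every rise | 9.5 | 11% | 29% |
| every rise above 0.5 | 14.5 | 24% | 36% |
| every rise above 1.0 | 17.7 | 36% | 42% |
| a quarter of rises above 0.5 | 18.6 | 40% | 43% |
| a quarter of rises above 1.0 | 19.4 | 44% | 45% |

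The last column gives both arms the placebo rate of worsening, so it isolates dilution. For every rise, dilution takes 46% to 29% and efficacy takes it on to 11%, about half the loss each.

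**Sensitivity to the assumed rates, all rises at each threshold recorded.** For 25% against 45%, power falls from 52% to 9–40%. For 45% against 65%, it falls from 46% to 16–39%. For 20% against 40%, it falls from 55% to 8–41%. For 10% against 20% with every rise recorded, the sign reverses: 31.8% on placebo, 29.2% on buspirone. With 20% in both arms, buspirone would look better by 2.5 to 10.2 points.

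**Event counts**, at one event per affected participant: the ratio without worsening is 0.55/0.35 = 1.57. With every rise recorded it is (0.55 + 0.115)/(0.35 + 0.242) = 1.12; with rises above 1.0 it is (0.55 + 0.014)/(0.35 + 0.045) = 1.43.

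**The case against.** A reader might infer that the plan hides drug harms, or that the adverse event tests lose most of their ability to show one. The documents do not support either as a general statement.

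- **Harms stay visible.** The 9.4.4 listing shows each event by name, class, arm and relatedness, so an excess of dizziness on buspirone could be seen there. The side-effect questionnaire asks directly about the complaints most likely to come from the drug; only nausea and upset stomach overlap with the disease. The causality scale in 8.3.3.2 already lets the clinician attribute an event to underlying disease. Laboratory, weight and ECG changes are compared by arm.
- **The size is mostly assumption.** Nothing links a rise in the PAGI-SYM score to an adverse event report. Section 8.2 describes the adverse event form more narrowly than 8.3.4, and no threshold for deterioration is given. The any-rise case counts one item moving one step. A large loss appears only when every small rise is recorded.
- **The comparison is not wrong.** Section 8.3.1 defines adverse events regardless of cause, and fewer worsening events on an effective drug is a true all-cause result. Nor does the plan rest tolerability on the any-event test, which has only 46% power for a 20-point excess even when worsening is separated.

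All of this limits the claim. What remains is that the safeguards lie outside the planned tests. The listing is for the monitoring board, and 9.4.8 keeps individual data with IDs out of manuscripts. No test uses relatedness, and 9.4.4 names no analysis of the questionnaire. Laboratory, weight and ECG comparisons cannot show dizziness, drowsiness or headache.

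**Conclusion.** The point holds in a limited form. Sections 8.3.4 and 9.4.4 together put worsening of the entry disease into every by-arm adverse event test. If buspirone works, those tests shift toward no excess on buspirone; if it does not, they are diluted.

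The direction follows from the text. The size does not: the rates of other events, their independence from worsening, normality of change and the share of worsening recorded are all assumed. Under 35% against 55%, power falls from 46% to anywhere between 11% and 44%, and part of each loss is dilution rather than efficacy. These figures use the fullness subscore alone; worsening of nausea, vomiting or pain would add events that cannot be sized from the documents.

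This is a gap in the planned summaries. It is not evidence that harms would go unseen.

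**What to change.** Keep the recording rule in 8.3.4. In 9.4.4:

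1. Prespecify each by-arm comparison (any event, number of events, highest grade, rate) for three sets: all adverse events; worsening of a PAGI-SYM symptom present at screening; and all other adverse events. Define the second set by a flag completed under masking, or derive it from the event term before unmasking.
2. Add a by-arm comparison of the side-effect questionnaire, which is already collected.
3. State that the tolerability conclusion is read from these results together, not from all adverse events alone.

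The cost is one check-box or a derivation rule, two extra rows in each table, and one further comparison on existing data. No visit, treatment or sample size changes. The downside is that nausea or upset stomach caused by the drug may be classed as disease, which is why all three sets are shown.

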8.3.5 ADVERSE EVENT REPORTING

The GpCRC BESST Trial will monitor and report adverse events to ensure participant safety. There are two separate sets of government regulations that apply to unanticipated or adverse events in research studies: (1) 45 CFR Part 46, Subpart A: the Common Rule,⁴² shared by 17 Departments and Agencies and (2) 21 CFR 312,⁴¹ the FDA regulation for adverse events. The Common Rule requires written procedures and policies for ensuring reporting of unanticipated problems involving risks to participants to IRBs, appropriate institutional officials, and the Department or Agency Head. The FDA regulation requires notification of the FDA and participating investigators of any adverse event associated with the use of a test article that is both serious and unexpected. Investigators should refer to the 2009 FDA guidance Improving Human Subjects Protection,⁴³ for adverse events reportable to their institutional IRB. Since the definitions and reporting requirements for unanticipated events differ between the two sets of Federal regulations, the GpCRC BESST Trial definitions and procedures for adverse events are designed to satisfy both sets of requirements.

Adverse events will be recorded on the Adverse Event data forms whether or not they are thought to be associated with the study or with the study drug. Adverse events may be discovered during regularly scheduled visits or through unscheduled participant contacts between visits. Summary data on adverse events will be monitored by the DSMB quarterly and at its semi-annual meetings or more frequently, as needed. These summaries will include analyses comparing rates of adverse events by treatment group, by clinic, or in other subgroups requested by the DSMB. Where applicable, signs and symptoms associated with the adverse event will be graded as to severity by the clinical site staff as mild, moderate, or severe using the Common Terminology Criteria for Adverse Events version CTCAE v5.0.

After each meeting, the DSMB will issue a written summary of its review of the study data, including adverse events, for transmission to the IRBs at each of the study centers. Analyses or listings of adverse events will not be provided to the IRBs; however, adverse events involving unanticipated problems involving risks to participants, or breaches of protocol which might entail risk to participants must be reported to local IRBs as soon as possible after they are discovered. Each participating center is responsible for ensuring that all local IRB requirements for reporting adverse events are met. A summary of adverse events will be reported to the FDA as part of the IND annual report.

8.3.6 SERIOUS ADVERSE EVENT REPORTING

Serious adverse events (SAE) must be reported upon discovery at the clinical center per local IRB guidelines. This will involve completing an Adverse Event (AE) data form describing the severity and details of the serious adverse event. This must be submitted to the SDRC within one business day for review by the Medical Safety Officer. **If the serious adverse event is judged by the study physician to be unexpected with a reasonable possibility of being caused by the buspirone study drug**, then the investigator must also submit to the SDRC a SAE/IND Safety Report (SR) form, along with a narrative summarizing the circumstances of the event, the current status of the participant, and a copy of the IRB report within two working days. The SDRC will submit a preliminary report to the NIDDK for review within three calendar days of receiving the SAE/IND Safety Report (SR) form. The pharmaceutical manufacturer will be notified within one working day but no longer than three calendar days of all fatal/life threatening serious adverse events, regardless of association to study drug,

If NIDDK determines that the SAE requires an expedited IND Safety Report, the NIDDK Program Official or the NIDDK Regulatory Affairs Specialist will notify the FDA no more than 15 calendar days from the initial receipt of the SAE by the SDRC (no later than 7 calendar days if the SAE is fatal or life threatening). The clinical center investigator may also be responsible for completing an FDA MedWatch 3500 form and additional information for a follow-up SAE report as information becomes available. If the FDA determines that a change to the Investigators Brochure, IND or protocol is needed, the SDRC will send a copy of the IND Safety Report to all clinical centers, with

instructions to forward the report to their IRB. NIDDK will determine if the DSMB members should be made aware of the event at that time, or it is appropriate to wait until the next DSMB meeting.

The SDRC will maintain a list of all SAEs for reporting and review at Steering Committee meetings and DSMB meetings. The DSMB will review all SAE reports, at least twice a year. On a case-by-case basis, the NIDDK program staff, in conjunction with the DSMB chairperson, will determine whether the DSMB should review SAE reports more efficaciously. The DSMB will review each SAE report and provide comments to the NIDDK Program Official. If requested by any member of the DSMB, a teleconference will be scheduled to discuss the SAE and recommend any actions to the NIDDK. The clinical center must submit to the NIDDK and to the Scientific Data Research Center a follow-up memo within one month of the SAE (and periodic updates if needed) to report the details of the disposition of the SAE.

The SDRC will provide to the pharmaceutical manufacturer copies of all SAEs regardless of association to buspirone study drug which involve disability, congenital anomaly/birth defects/fetal losses, hospitalizations, and important medical events, such as cancers with no prior history within five calendar days of receipt. In addition, the SDRC will report any pregnancy occurring in association with the use of study drug to the pharmaceutical manufacturer within three calendar days. The SDRC will report overdoses of the buspirone study drug to the pharmaceutical manufacturer every six months. An overdose that results in an SAE or is associated with an SAE, will follow the normal SAE reporting process and timeframe.

